Safety and efficacy endpoints will be displayed using descriptive statistics and graphical displays, where applicable. For categorical variables, frequencies, and percentages will be presented. The denominators for percentages will be based on the number of subjects appropriate for the purpose of analysis. Continuous variables will be summarized using descriptive statistics (number of subjects, mean, median, standard deviation (SD), minimum, and maximum). Where relevant, 95% confidence intervals will be calculated. All statistical tests of the primary and secondary endpoints will be conducted at the 0.05 significance level using 2-tailed tests. Nominal p-values will be reported for treatment comparisons of the exploratory endpoints.

The study treatment period is defined from randomization through completion of Week 12/ET1 visit and the safety follow-up period is from the completion of Week 12 through the completion of Week 24/ET2 visit.

The analysis populations include the following:

Safety Population (SAF): The Safety population will consist of all subjects who receive at least one application of study medication.

Intent-To-Treat Population (ITT): The ITT population will consist of all subjects who are randomized.

Per-Protocol Population (PP): The PP population will consist of all subjects in the ITT population who had no significant protocol deviations that impacted the analyses of the efficacy endpoints.

The primary efficacy endpoint, proportion of subjects with complete clearance of all treatable molluscum lesions at Week 12 in the ITT, will be analyzed using a generalized estimating equation (GEE) for logistic regression with an exchangeable working correlation structure. The model will include treatment, investigator type (dermatologist vs other), household number of randomized subjects (1 subject per household vs 2 subjects per household), age and Baseline lesion count as factors. The odds ratio between SB206 12% and vehicle gel, 95% CIs for the odds ratio, and *P*-value for the covariate-adjusted treatment comparison will be presented. Only subjects who achieve complete clearance at Week 12 will be counted as responders for the primary analysis; all other subjects (e.g., those

who discontinue the study before achieving complete clearance) will be reported as failures. As a sensitivity analysis, the primary efficacy analysis will also be reported for the PP population.

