11 STATISTICS

11.1 General Procedures

The study treatment period is defined from randomization through completion of Week 12/ET1 visit and the safety follow-up period is from the completion of Week 12 through the completion of Week 24/ET2 visit.

After all subjects have completed their Week 12/ET1 visit, thus completing the Treatment Period of the study, the database through Week 12/ET1 will be frozen and unblinded for purposes of the primary analysis of efficacy and safety. While this analysis is being prepared, the subjects will continue through Week 24/ET2. After all subjects have completed their Week 24/ET2 visit, the database will be locked and the follow-up data will be analyzed. Prior to unblinding and the primary analysis of efficacy and safety, a detailed, finalized SAP will be completed and placed on file. The Statistical Analysis Plan will contain a more comprehensive explanation than that provided here of the methodology used in the statistical analyses, as well as the rules and data handling conventions used to perform the analyses and the procedure used to account for missing data.

Safety and efficacy endpoints will be displayed using descriptive statistics and graphical displays, where applicable. For categorical variables, frequencies, and percentages will be presented. The denominator for percentage will be based on the number of subjects appropriate for the purpose of analysis. Continuous variables will be summarized using descriptive statistics (number of subjects, mean, median, standard deviation [SD], minimum, and maximum). Where relevant, 95% confidence intervals will be calculated. Any statistical tests will be conducted at the 0.05 significance level using 2-tailed tests, and nominal p-values will be reported.

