6. GENERAL ANALYSIS CONSIDERATIONS

The statistical analyses will be reported using summary tables, listings, and figures (TLFs). The International Council for Harmonisation (ICH) numbering convention will be used for all TLFs. Unless otherwise noted, all statistical testing will be 2-sided and will be performed at the 0.05 significance level. Tests will be declared statistically significant if the calculated *P*-value is ≤ 0.05 .

Continuous variable summaries will include the number of subjects (n) with non-missing values, mean, standard deviation (SD), median, minimum, and maximum. Other statistics such as quartiles, confidence intervals (CIs), and number of missing values may be added as appropriate.

Categorical variable summaries will include the frequency and percentage of subjects who are in the category or each possible value. In general, the denominator for the percentage calculation will be based upon the total number of subjects in the study population within each treatment group, unless otherwise specified. The denominator for by-visit displays will be the number of subjects in the relevant study population with non-missing data at each visit.

All summary tables will be presented by treatment group. Baseline summaries will also include an overall summary column.

Individual subject data obtained from the eCRFs and any derived data will generally be presented by subject in data listings. Additionally, a listing of the subjects requiring a narrative because they experience one of the following events: serious adverse event, death, discontinued the study due to an AE, hypertrophic or keloid scarring, unresolved scars, or LSR suggestive of allergic contact dermatitis will be presented.

The analyses described in this plan are considered a priori, in that they have been defined prior to breaking the blind.

Any analyses performed subsequent to breaking the blind will be considered post hoc and exploratory. Post hoc analyses will be labeled as such on the output and identified in the clinical study report.

All analyses and tabulations will be performed using SAS® software Version 9.4 or higher. Tables, listings, and figures will be presented in RTF format.

The process for SAS program validation and quality control (QC) for programs and outputs is documented in the Synteract working instruction “SAS programming quality control.” Study-specific QC requirements can be found in [Appendix C: SAS Programming QC Requirements](#).

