10.1 Efficacy Endpoints

The primary efficacy endpoint is the proportion of subjects with complete clearance of all treatable MC at Week 12.

The secondary efficacy endpoint is the proportion of subjects with complete clearance of all treatable MC at Week 8.

Complete clearance is defined as having a total number of lesions count of 0.

The exploratory endpoints are the following:

- Proportion of subjects with complete clearance of all treatable MC at Week 2 and Week 4 visits
- Proportion of subjects achieving at least a 95% reduction from Baseline in the number of all treatable MC at each visit (Weeks 2, 4, 8, 12)
- Proportion of subjects achieving at least a 90% reduction from Baseline in the number of all treatable MC at each visit (Weeks 2, 4, 8, 12)
- Proportion of subjects achieving at least a 75% reduction from Baseline in the number of all treatable MC at each visit (Weeks 2, 4, 8, 12)
- Percent change from Baseline in number of treatable MC at each visit (Weeks 2, 4, 8, 12)
- Change from Baseline in number of treatable MC at each visit (Weeks 2, 4, 8, 12)
- Proportion of subjects who have a recurrence of MC after the first visit at which complete clearance was observed, defined as the total lesion count being greater than 0 at any point after achieving a count of 0

- Time to complete clearance of all treatable MC, defined as the days between the date of first dose and the first date of clearance. Subjects who do not achieve complete clearance will be censored at the date of the last lesion count assessment.
- Proportion of subjects with scarring, defined as an answer of Yes to either question on the Scarring/Keloid Assessment eCRF page: “Was the presence of a scar > 1 mm deep and/or 5 mm wide noted?” or “Was the presence of a scar noted?”, after clearance of lesion(s) at each visit (Weeks 4, 8, 12, 24)
- Proportion of subjects with keloid or hypertrophic scar, defined as an answer of Yes to the Scarring/Keloid Assessment eCRF page question “Was the presence of a keloid or hypertrophic scar noted?”, after clearance of lesion(s) at each visit (Weeks 4, 8, 12, 24)
- Change from Baseline of the composite score from age-matched (at Baseline) Dermatology Life Quality Index (DLQI) or Children’s Dermatology Life Quality Index (CLDQI) assessment at Week 12
- Subject-reported spread to household members as measured by any new occurrence of MC in household members of subjects at each visit (Weeks 2, 4, 8, 12, 16, 20, 24)

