10.7 Multiple Comparison/Multiplicity

The familywise error rate with respect to the primary endpoint and secondary endpoint will be strongly controlled at the alpha=0.05 level using a fixed-sequence method testing strategy. If the primary endpoint is not statistically significant at the alpha=0.05 level, the secondary efficacy endpoint will be considered not significant. If the primary endpoint is statistically significant at the alpha=0.05 level, then the secondary efficacy endpoint will be analyzed. If the secondary efficacy endpoint fails to reach statistical significance at the alpha=0.05 level, it will be considered not statistically significant.

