11.3 Exploratory Analyses

The exploratory endpoints based on the proportion of subjects achieving complete clearance or 75%, 90%, or 95% reductions will be analyzed in the same manner as the primary endpoint.

Since the within-household correlation is expected to be small and the change and percent change from Baseline in the number of treatable MC are exploratory, they will be analyzed using a repeated measures mixed model for the respective visits with the same covariates as the primary model together with visits and treatment by visit; an unstructured covariance matrix will be utilized. If the calculation of the percent change from baseline is influenced by outliers with calculated values >100%, then the influence of outliers will be avoided for analysis by censoring them so that all values were in the range of -100% to 100%. If the model fails to converge, then other correlation structures will be explored.

Since the within-household correlation is expected to be small and time to first complete clearance of all MC is exploratory, it will be analyzed using Kaplan-Meier methods. The number and percentage of subjects achieving complete clearance, number and percentage of censored subjects, and Kaplan-Meier estimates of first quartile, median, and third quartile will be summarized by treatment group. Differences in Kaplan-Meier curves between the treatments will be tested for significance using a stratified log-rank test.

The proportion of subjects with scarring and the proportion of subjects with keloid or hypertrophic scarring will be summarized descriptively at each visit.

The change from Baseline of the composite score from age-matched (at Baseline) DLQI/CDLQI will be summarized descriptively and separately for each questionnaire. The scoring algorithms are detailed in [Appendix A](#). The CDLQI will be examined in the following Week 12 response categories: complete clearance, 95% reduction in lesion counts, 90% reduction in lesion counts, and subjects who did not achieve complete clearance. Additionally, the changes from Baseline in the following subscales: Symptoms and Feelings, Daily Activities, Leisure, Work and School, Personal Relationships, and Treatment, for DLQI, and Symptoms and Feelings, Leisure, School or Holidays, Personal Relationships, Sleep, and Treatment, for CDLQI, and each question will be summarized descriptively.

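### SAP section 6 lets exploratory tests be declared statistically significant at P ≤ 0.05, although the protocol synopsis makes their p-values nominal

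*Combined protocol and SAP*

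**What the plan says.** The passages that bear on the status of the exploratory tests are these.

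- **Protocol synopsis, Statistical Methods.** The 0.05 level is attached to tests of the primary and secondary endpoints. For the rest: "Nominal p-values will be reported for treatment comparisons of the exploratory endpoints".
- **Protocol 11.1.** One sentence covers everything: "Any statistical tests will be conducted at the 0.05 significance level using 2-tailed tests, and nominal p-values will be reported".
- **Final SAP, section 6.** The general rule reads: "all statistical testing will be 2-sided and will be performed at the 0.05 significance level. Tests will be declared statistically significant if the calculated". The cut-off that follows is 0.05 or less. A qualifier allowing for noted exceptions opens the first of these two sentences; the second, on declaring significance, carries none of its own.
- **Final SAP, 10.7.** "The familywise error rate with respect to the primary endpoint and secondary endpoint will be strongly controlled at the alpha=0.05 level", by a fixed sequence. The gate is explicit: "If the primary endpoint is not statistically significant at the alpha=0.05 level, the secondary efficacy endpoint will be considered not significant". Exploratory endpoints are not mentioned.
- **Final SAP, 11.3.** Clearance at Weeks 2 and 4 and the 75%, 90% and 95% reductions use the primary endpoint's model. Change and percent change use a mixed model with treatment by visit. For time to clearance: "Differences in Kaplan-Meier curves between the treatments will be tested for significance using a stratified log-rank test".
- **Final SAP, section 14.** The list of departures from the protocol includes the new 90% and 95% endpoints. It says nothing about the status of exploratory p-values.

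**The concern.** The synopsis separates tests that lead to a declaration from tests that yield a nominal p-value. SAP section 6 has one rule for all tests. Its opening qualifier would help only if an exception were noted somewhere, and for the exploratory efficacy endpoints none is. SAP 10.7 deals with the secondary endpoint alone. SAP 10.8 warns about chance findings, but only for pooled centres.

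The problem shows if the primary endpoint fails. SAP 10.7 then requires Week 8 clearance to be called not significant, whatever its p-value. Section 6 would still allow a 95% reduction at Week 8 to be declared significant. For many subjects these are the same outcome. With 3 to 19 lesions at baseline, one remaining lesion is at least 1/19 = 5.3% of baseline, so a 95% reduction requires a count of zero. A report that followed the SAP could therefore claim statistical significance on a close substitute for an endpoint that the gate had closed.

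**Working it through.** **1. The controlled family.** The only family-wise rate in the documents is 0.05 for primary plus secondary, and it holds. If the primary null is true, any false rejection in this family requires the primary to be rejected, with probability at most 0.05. If only the secondary null is true, the sole possible error is rejecting the secondary, again at most 0.05. Exploratory tests do not enter this calculation.

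**2. Number of ungated exploratory comparisons (final SAP 10.1 and 11.3).**

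| Endpoint | Tests |
|---|---|
| Complete clearance, Weeks 2 and 4 | 2 |
| 95%, 90%, 75% reduction × 4 visits | 12 |
| Time to clearance, log-rank | 1 |
| *Subtotal* | *15* |
| Change and percent change × 4 visits | 8 |
| *Total* | *23* |

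The last eight count only if each visit contrast of the mixed model is tested, which 11.3 does not say outright. Eight of the 12 reduction tests (90% and 95%) were added in the final SAP.

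**3. Chance of at least one P ≤ 0.05 when the drug has no effect.** Take k standard normal test statistics with common correlation ρ and c = 1.96. Write

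g(x) = Φ((c − √ρ·x)/√(1−ρ)) − Φ((−c − √ρ·x)/√(1−ρ)).

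Then

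- P(any exploratory) = 1 − ∫ g(x)^k φ(x) dx
- P(primary fails and any exploratory) = 0.95 − ∫ g(x)^(k+1) φ(x) dx, with the primary sharing the same ρ.

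The documents give no ρ, so the range is shown.

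| ρ (assumed) | Any, k = 23 | Primary fails and any, k = 23 | Any, k = 15 | Primary fails and any, k = 15 |
|---|---|---|---|---|
| 0 | 69% | 66% | 54% | 51% |
| 0.3 | 58% | 54% | 46% | 43% |
| 0.5 | 45% | 41% | 36% | 32% |
| 0.7 | 31% | 26% | 26% | 21% |
| 0.9 | 16% | 11% | 14% | 10% |

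Check at ρ = 0: 1 − 0.95^23 = 0.693 and 1 − 0.95^15 = 0.537.

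**4. Check with a less artificial correlation structure.** Lesion counts were simulated under no effect with 227 and 113 subjects, four visits and 4,000 runs per setting. Assumed clearance was 2/6/12/20% at Weeks 2/4/8/12. Tests were unadjusted, without household clustering. With between-visit correlation of 0.5, 0.7, 0.85 and 0.95, at least one of the 23 tests reached P ≤ 0.05 in 45%, 39%, 35% and 31% of runs. The primary failed and at least one did so in 40%, 35%, 30% and 26%. These figures lie inside the range above.

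**The case against.** The strongest reply is that the protocol already settles the matter. The synopsis says nominal, protocol 11.1 uses the same word, and the SAP goes on calling these endpoints exploratory. Because section 14 does not list dropping the nominal rule, the natural reading is that it still applies. The section 6 wording is also not new: it stands in the two earlier SAP versions, and protocol 11.1 already puts any test at the 0.05 level. So this is a wording gap, not a deliberate change.

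Much of that stands. The documents do not show an intention to make the exploratory tests confirmatory. SAP 11.3's reference to the primary endpoint's manner of analysis describes the model, and its phrase about testing Kaplan-Meier curves is ordinary log-rank language. The table shells are in a separate file and may already carry suitable footnotes.

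What the reply does not remove is the conflict. Section 6 is not silent: it states when a test is declared significant. Protocol 11.1 cannot resolve the matter, because it puts every test at 0.05 and calls every p-value nominal in one sentence. Protocol 12.1.2 leaves the exploratory methods to the SAP, so a report writer would look there and find only the rule in section 6.

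**Conclusion.** The conflict is real and should be corrected. It concerns what the report may declare, not the validity of the primary test.

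The size depends on an assumption. For a common correlation of 0.3 to 0.9, the chance of at least one exploratory declaration under a global null is about 58% to 16% for 23 tests and 46% to 14% for 15. The chance that the primary also fails is about 54% to 11% for 23 tests. Even the lowest of the any-declaration figures is nearly three times the 0.05 at which each test is run.

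Two stronger readings are not supported. A reader might infer that the fixed sequence is broken, or that the trial's family-wise error is inflated. It is not: SAP 10.7 claims control for the primary and secondary only, and that error stays at 0.05. A reader might also quote a single figure such as 45%. That value needs a correlation near 0.5, which no document gives, and it is the chance of any exploratory declaration. The chance of one together with a failed primary, at the same correlation, is 41%.

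**What to change.** 1. In SAP section 6, replace the declaration sentence with: *Statistical significance (two-sided P ≤ 0.05) will be declared only for the primary endpoint and, if the primary is significant, for the secondary endpoint (section 10.7). All other p-values are nominal and will not be described as statistically significant.*
2. In SAP 11.3, reword the log-rank sentence so that the Kaplan-Meier curves are compared, with a nominal p-value.
3. Align protocol 11.1 with the synopsis.
4. Check that the shells for the exploratory tables label their p-values as nominal and unadjusted, and add a footnote if they do not.

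The cost is a few sentences. Data, sample size and the primary test are unchanged. The one downside is that exploratory results can no longer be reported as statistically significant, which is what the synopsis already implies.

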7. NOTATION OF TREATMENT GROUPS AND VISITS

Analysis visits

Baseline is defined as the last nonmissing value recorded prior to the first application of study drug. If time is not recorded and the assessment was on the same day as the first application of study drug, then it will be assumed the assessment occurred prior to the application of study drug. The baseline record will have an analysis visit of “Baseline”.

For all evaluations of all parameters, assessments will be analyzed according to the visit at which they occurred (i.e., per the eCRF visit label). In order to account for the fact that the Week 12 and Early Termination visits are collected on the same eCRF in the database, a check against the Study Exit form will be made to determine if the visit is a Week 12 or an Early Termination Visit. If the visit is an Early Termination visit, then the visit will be mapped according to the table below. If there is no corresponding Study Exit form on the same date, then it will be considered a Week 12 visit. If there is no assessment in a given visit, then the following visit windows will be applied to determine if an unscheduled visit may be used:

Visit	Analysis Visit	Target Study Day	Study Day Analysis Window
Week 2 (± 3 days)	Week 2	15	Day 12 to 22
Week 4 (± 5 days)	Week 4	29	Day 23 to 43
Week 8 (± 5 days)	Week 8	57	Day 44 to 71
Week 12 (± 5 days)	Week 12	85	Day 72 to 98

Days are measured from the date of randomization. Study days corresponding to measurements are calculated as:

- Assessment date – date of randomization + 1, if assessment date is on or after the date of randomization.
- Assessment date – date of randomization, if measurement date is before the date of randomization.

In the event of multiple unscheduled records falling in the same analysis window, the assessment which is closest to the target study day will be chosen for analysis.

